#### 6.6.4. Electrocardiograms

Values and changes from baseline in ECG parameters will be summarized as continuous variables by treatment group at Baseline and EOT of the on-treatment safety analysis period for the safety analysis set. Results for overall are only shown at Baseline.

ECG abnormalities during on-treatment period will be summarized by treatment group as the number and percentage of participants in the following categories:

- QTcF (msec): > 450 to 480, > 480 to 500, > 500.
- QTcF interval increase from baseline (msec): > 30 to 60, >60.

#### 6.6.5. Columbia Suicide Severity Rating Scale (C-SSRS)

Frequency table by treatment group will be provided for C-SSRS suicidality on-treatment period in the safety analysis set.

### 7. INTERIM ANALYSES

#### 7.1. Introduction

No interim analysis will be conducted for this study.

#### 7.2. Interim Analyses and Summaries

Not applicable.

### 8. REFERENCES

## 9. APPENDICES

### Appendix 1. Summary of Efficacy Analyses

Endpoint	Analysis Type	Population	Data Inclusion and Rules for Handling Intercurrent Events and Missing Data	Analysis Model
Percentage of participants with pain freedom at 2 hours postdose	Main analysis for the co-primary endpoints	EAS	Taking rescue medication at or before 2 hours postdose or missing pain intensity at 2 hours postdose will be regarded as failures.	Mantel-Haenszel risk estimation stratified by country/region at randomization
	Sensitivity analysis	EAS	Taking rescue medication at or before 2 hours postdose will be regarded as a failure. Missing data will be imputed.	Copy from reference multiple imputation approach
	Sensitivity analysis	EAS	Taking rescue medication at or before 2 hours postdose will be regarded as a failure. Missing data will be imputed.	Varying response rates for imputation
Percentage of participants with an MBS reported before dosing that is absent at 2 hours postdose	Main analysis for the co-primary endpoints	EAS	Taking rescue medication at or before 2 hours postdose or missing MBS status at 2 hours postdose will be regarded as failures.	Mantel-Haenszel risk estimation stratified by country/region at randomization
	Sensitivity analysis	EAS	Taking rescue medication at or before 2 hours postdose will be	Copy from reference multiple

Endpoint	Analysis Type	Population	Data Inclusion and Rules for Handling Intercurrent Events and Missing Data	Analysis Model
			regarded as a failure. Missing data will be imputed.	imputation approach
	Sensitivity analysis	EAS	Taking rescue medication at or before 2 hours postdose will be regarded as a failure. Missing data will be imputed.	Varying response rates for imputation
Percentage of participants with a pain intensity of none or mild at 15 minutes postdose	Secondary analysis	EAS	Taking rescue medication at or before 15 minutes postdose or missing pain intensity at 15 minutes postdose will be regarded as failures.	Mantel-Haenszel risk estimation stratified by country/region at randomization
Percentage of participants with a pain intensity of none or mild at 30 minutes postdose	Secondary analysis	EAS	Taking rescue medication at or before 30 minutes postdose or missing pain intensity at 30 minutes postdose will be regarded as failures.	Mantel-Haenszel risk estimation stratified by country/region at randomization
Percentage of participants with a pain intensity of none or mild at 2 hours postdose	Secondary analysis	EAS	Taking rescue medication at or before 2 hours postdose or missing pain intensity at 2 hours postdose will be regarded as failures.	Mantel-Haenszel risk estimation stratified by country/region at randomization
Return to normal function at 2 hours postdose	Secondary analysis	EAS with functional disability at	Taking rescue medication at or before 2 hours postdose or missing functional disability level at 2 hours	Mantel-Haenszel risk estimation stratified by

Endpoint	Analysis Type	Population	Data Inclusion and Rules for Handling Intercurrent Events and Missing Data	Analysis Model
		time of dosing	postdose will be regarded as failures.	country/region at randomization
Percentage of participants with a pain intensity of none or mild at all time points from 2 to 24 hours postdose	Secondary analysis	EAS	(1) Taking rescue medication at or before 24 hours postdose, (2) missing pain intensity at 2 or 24 hours postdose, or (3) missing pain intensity at > 1 time point from 3 to 8 hours postdose will be regarded as failures.	Mantel-Haenszel risk estimation stratified by country/region at randomization
Percentage of participants with a pain intensity of none or mild at all time points from 2 to 48 hours postdose	Secondary analysis	EAS	(1) Taking rescue medication at or before 48 hours postdose, (2) missing pain intensity at 2, 24 or 48 hours postdose, or (3) missing pain intensity at > 1 time point from 3 to 8 hours postdose will be regarded as failures.	Mantel-Haenszel risk estimation stratified by country/region at randomization
Return to normal function at 30 minutes postdose	Secondary analysis	EAS with functional disability at time of dosing	Taking rescue medication at or before 30 minutes postdose or missing functional disability level at 30 minutes postdose will be regarded as failures.	Mantel-Haenszel risk estimation stratified by country/region at randomization
Return to normal function at 60 minutes postdose	Secondary analysis	EAS with functional disability at	Taking rescue medication at or before 60 minutes postdose or missing functional disability level at	Mantel-Haenszel risk estimation stratified by

Endpoint	Analysis Type	Population	Data Inclusion and Rules for Handling Intercurrent Events and Missing Data	Analysis Model
		time of dosing	60 minutes postdose will be regarded as failures.	country/region at randomization
Freedom from phonophobia at 2 hours postdose	Secondary analysis	EAS with phonophobia present at time of dosing	Taking rescue medication at or before 2 hours postdose or missing phonophobia status at 2 hours postdose will be regarded as failures.	Mantel-Haenszel risk estimation stratified by country/region at randomization
Freedom from photophobia at 2 hours postdose	Secondary analysis	EAS with photophobia present at time of dosing	Taking rescue medication at or before 2 hours postdose or missing photophobia status at 2 hours postdose will be regarded as failures.	Mantel-Haenszel risk estimation stratified by country/region at randomization
Freedom from nausea at 2 hours postdose	Secondary analysis	EAS with nausea present at time of dosing	Taking rescue medication at or before 2 hours postdose or missing nausea status at 2 hours postdose will be regarded as failures.	Mantel-Haenszel risk estimation stratified by country/region at randomization
Percentage of participants with pain freedom at all time points from 2 to 24 hours postdose	Secondary analysis	EAS	(1) Taking rescue medication at or before 24 hours postdose, (2) missing pain intensity at 2 or 24 hours postdose, or (3) missing pain intensity at > 1 time point from 3 to 8 hours postdose will be regarded as failures.	Mantel-Haenszel risk estimation stratified by country/region at randomization

Endpoint	Analysis Type	Population	Data Inclusion and Rules for Handling Intercurrent Events and Missing Data	Analysis Model
Percentage of participants with pain freedom at all time points from 2 to 48 hours postdose	Secondary analysis	EAS	(1) Taking rescue medication at or before 48 hours postdose, (2) missing pain intensity at 2, 24 or 48 hours postdose, or (3) missing pain intensity at > 1 time point from 3 to 8 hours postdose will be regarded as failures.	Mantel-Haenszel risk estimation stratified by country/region at randomization
Percentage of participants with pain relapse at any time point after 2 hours postdose	Secondary analysis	EAS with pain freedom at 2 hours postdose	Taking rescue medication at or before 48 hours postdose or missing pain intensity at >1 time point from 3 to 48 hours postdose will be regarded as failures.	Mantel-Haenszel risk estimation stratified by country/region at randomization
Percentage of participants taking rescue medication within 24 hours postdose	Secondary analysis	EAS	Observed data	Mantel-Haenszel risk estimation stratified by country/region at randomization
	Supportive analysis	EAS	Observed data	Time-to-event
Percentage of participants with a pain intensity of none or mild at 60 minutes postdose	Secondary analysis	EAS	Taking rescue medication at or before 60 minutes postdose or missing pain intensity at 60 minutes postdose will be regarded as failures.	Mantel-Haenszel risk estimation stratified by country/region at randomization

Endpoint	Analysis Type	Population	Data Inclusion and Rules for Handling Intercurrent Events and Missing Data	Analysis Model
Return to normal function at 15 minutes postdose	Secondary analysis	EAS	Taking rescue medication at or before 15 minutes postdose or missing functional disability level at 15 minutes postdose will be regarded as failures.	Mantel-Haenszel risk estimation stratified by country/region at randomization
Percentage of participants with pain freedom at 15 minutes, 30 minutes, 45 minutes, 60 minutes, 90 minutes, 2 hours, 3 hours, 4 hours, 6 hours, 8 hours, 24 hours and 48 hours	Exploratory analysis	EAS	Taking rescue medication at or before each of the assessed time points postdose or missing pain intensity at each of the assessed time points postdose respectively will be regarded as failures.	Mantel-Haenszel risk estimation stratified by country/region at randomization
	Supportive analysis	EAS	Observed data	Time-to-event Kaplan-Meier
Percentage of participants with an MBS reported before dosing that is absent at 15 minutes, 30 minutes, 45 minutes, 60 minutes, 90 minutes, 2 hours, 3 hours, 4 hours, 6 hours, 8 hours, 24 hours and 48 hours	Exploratory analysis	EAS	Taking rescue medication at or before each of the assessed time points postdose or missing MBS status at each of the assessed time points postdose respectively will be regarded as failures.	Mantel-Haenszel risk estimation stratified by country/region at randomization
	Supportive analysis	EAS with MBS reported on	Observed data	Time-to-event Kaplan-Meier

Endpoint	Analysis Type	Population	Data Inclusion and Rules for Handling Intercurrent Events and Missing Data	Analysis Model
		study before dosing		
Percentage of participants with a pain intensity of none or mild at 15 minutes, 30 minutes, 45 minutes, 60 minutes, 90 minutes, 2 hours, 3 hours, 4 hours, 6 hours, 8 hours, 24 hours and 48 hours	Exploratory analysis	EAS	Taking rescue medication at or before each of the assessed time points postdose or missing pain intensity at each of the assessed time points postdose respectively will be regarded as failures.	Mantel-Haenszel risk estimation stratified by country/region at randomization
	Supportive analysis	EAS	Observed data	Time-to-event Kaplan-Meier
Percentage of participants with a functional disability level of normal at 15 minutes, 30 minutes, 45 minutes, 60 minutes, 90 minutes, 2 hours, 3 hours, 4 hours, 6 hours, 8 hours, 24 hours and 48 hours	Exploratory analysis	EAS with functional disability at the time of dosing	Taking rescue medication at or before each of the assessed time points postdose or missing functional disability level at each of the assessed time points postdose respectively will be regarded as failures.	Mantel-Haenszel risk estimation stratified by country/region at randomization
	Supportive analysis	EAS with functional disability at	Observed data	Time-to-event Kaplan-Meier

Endpoint	Analysis Type	Population	Data Inclusion and Rules for Handling Intercurrent Events and Missing Data	Analysis Model
		the time of dosing		
Percentage of participants with phonophobia absent at 15 minutes, 30 minutes, 45 minutes, 60 minutes, 90 minutes, 2 hours, 3 hours, 4 hours, 6 hours, 8 hours, 24 hours and 48 hours	Exploratory analysis	EAS with phonophobia present at the time of dosing	Taking rescue medication at or before each of the assessed time points postdose or missing phonophobia status at each of the assessed time points postdose respectively will be regarded as failures.	Mantel-Haenszel risk estimation stratified by country/region at randomization
	Supportive analysis	EAS with phonophobia present at the time of dosing	Observed data	Time-to-event Kaplan-Meier
Percentage of participants with photophobia absent at 15 minutes, 30 minutes, 45 minutes, 60 minutes, 90 minutes, 2 hours, 3 hours, 4 hours, 6 hours, 8 hours, 24 hours and 48 hours	Exploratory analysis	EAS with photophobia present at the time of dosing	Taking rescue medication at or before each of the assessed time points postdose or missing photophobia status at each of the assessed time points postdose respectively will be regarded as failures.	Mantel-Haenszel risk estimation stratified by country/region at randomization
	Supportive analysis	EAS with photophobia present at	Observed data	Time-to-event Kaplan-Meier

Endpoint	Analysis Type	Population	Data Inclusion and Rules for Handling Intercurrent Events and Missing Data	Analysis Model
		the time of dosing		
Percentage of participants with nausea absent at 15 minutes, 30 minutes, 45 minutes, 60 minutes, 90 minutes, 2 hours, 3 hours, 4 hours, 6 hours, 8 hours, 24 hours and 48 hours	Exploratory analysis	EAS with nausea present at the time of dosing	Taking rescue medication at or before each of the assessed time points postdose or missing nausea status at each of the assessed time points postdose respectively will be regarded as failures.	Mantel-Haenszel risk estimation stratified by country/region at randomization
	Supportive analysis	EAS with nausea present at the time of dosing	Observed data	Time-to-event Kaplan-Meier
Percentage of participants with the PGIC overall status improvement at 30 minutes, 60 minutes, 2 hours, and 24 hours postdose	Summary	EAS	Observed data	Mantel-Haenszel risk estimation stratified by country/region at randomization

## Appendix 2. Data Derivation Details

### Appendix 2.1. Endpoint Derivations

#### Appendix 2.1.1. Efficacy Endpoint Derivations

Let X denote a planned time point postdose: 15, 30, 45, 60, or 90 minutes; 2, 3, 4, 6, 8, 24, or 48 hours.

##### Pain Freedom over Time

At time point X, participants who meet both of the following criteria are classified as responders:

- Pain intensity of none at X, i.e., in the X analysis window
- No rescue medication taken at or before the pain intensity assessment in the X analysis window.

At time point X, participants who are not responders are classified as failures. Failure criteria include any of the following:

- Rescue medication taken at or before X (RM=F)
- Mild, moderate, or severe pain intensity at X
- Missing pain intensity at X (NC=F).

##### MBS Freedom over Time

At time point X, participants who meet both of the following criteria are classified as responders:

- MBS reported before dosing that is absent at X, i.e., in the X analysis window
- No rescue medication taken at or before the MBS status assessment in the X analysis window.

At time point X, participants who are not responders are classified as failures. Failure criteria include any of the following:

- Missing MBS before dosing
- Rescue medication taken at or before X (RM=F)
- MBS present at X, e.g., nausea reported as MBS before dosing and nausea status of present in the X analysis window
- Missing MBS at X (NC=F), e.g., nausea reported as MBS before dosing and missing nausea status in the X analysis window.

**Pain Relief over Time**

At time point X, participants who meet both of the following criteria are classified as responders:

- Pain intensity of none or mild at X, i.e., in the X analysis window
- No rescue medication taken at or before the pain intensity assessment in the X analysis window.

At time point X, participants who are not responders are classified as failures. Failure criteria include any of the following:

- Rescue medication taken at or before X (RM=F)
- Moderate or severe pain intensity at X
- Missing pain intensity at X (NC=F).

**Return to Normal Function over Time**

This endpoint is evaluated in the subset of participants with functional disability at the time of dosing.

At time point X, participants who meet both of the following criteria are classified as responders:

- Functional disability level of normal at X, i.e., in the X analysis window
- No rescue medication taken at or before the functional disability level assessment in the X analysis window.

At time point X, participants who are not responders are classified as failures. Failure criteria include any of the following:

- Rescue medication taken at or before X (RM=F)
- Functional disability level of mildly impaired, severely impaired, or requires bedrest at X
- Missing functional disability level at X (NC=F).

**Freedom from Photophobia, Phonophobia, or Nausea over Time**

Symptom freedom at a single time point postdose is defined as a symptom status of absent at that time point for the subset of participants with symptom status of present at the time of dosing.

For symptom freedom at X, participants who meet both of the following criteria are classified as responders:

- Symptom status of absent at X, i.e., in the X analysis window

- No rescue medication taken at or before the symptom status assessment in the X analysis window

For symptom freedom at X, participants who are not responders are classified as failures. Failure criteria include any of the following:

- Rescue medication taken at or before X (RM=F)
- Symptom status of present at X
- Missing symptom status at X (NC=F).

### **Sustained Pain Relief at 2 to 24 Hours Postdose**

Sustained pain relief from 2 to 24 hours postdose is defined as pain intensity of none or mild at all time points from 2 to 24 hours postdose.

Participants who meet all the following criteria are classified as responders:

- Pain intensity of none or mild at all time points from 2 to 24 hours postdose, i.e., in the 2 to 24-hour postdose analysis windows
- Missing pain intensity at  $\leq 1$  time point from 3 to 8 hours postdose, i.e., in the 3, 4, 6, or 8-hour postdose analysis windows
- No rescue medication taken at or before the pain intensity assessment in the 24-hour postdose analysis window.

Participants who are not responders are classified as failures. Failure criteria include any of the following:

- Rescue medication taken 24 hours postdose (RM=F)
- Moderate or severe pain intensity at any time point from 2 to 24 hours postdose, i.e., in the 2, 3, 4, 6, 8, or 24-hour postdose analysis window
- Missing pain intensity at 2 or 24 hours postdose (NC=F), i.e., in the 2 or 24-hour postdose analysis window
- Missing pain intensity at  $> 1$  time point from 3 to 8 hours postdose (NC1=F), i.e., in the 3, 4, 6, or 8-hour postdose analysis window.

### **Sustained Pain Relief from 2 to 48 Hours Postdose**

Sustained pain relief from 2 to 48 hours postdose is defined as pain intensity of none or mild at all time points from 2 to 48 hours postdose.

Participants who meet all the following criteria are classified as responders:

- Pain intensity of none or mild at all time points from 2 to 48 hours postdose, i.e., in the 2 to 48-hour postdose analysis windows

- Missing pain intensity at  $\leq 1$  time point from 3 to 8 hours postdose, i.e., in the 3, 4, 6, or 8-hour postdose analysis windows
- No rescue medication taken at or before the pain intensity assessment in the 48-hour postdose analysis window.

Participants who are not responders are classified as failures. Failure criteria include any of the following:

- Rescue medication taken at or before 48 hours postdose (RM=F)
- Moderate or severe pain intensity at any time point from 2 to 48 hours postdose, i.e., in the 2, 3, 4, 6, 8, 24, or 48-hour postdose analysis window
- Missing pain intensity at 2, 24, or 48 hours postdose (NC=F), i.e., in the 2, 24, or 48-hour postdose analysis window
- Missing pain intensity at  $> 1$  time point from 3 to 8 hours postdose (NC1=F), i.e., in the 3, 4, 6, or 8-hour postdose analysis window.

### **Sustained Pain Freedom from 2 to 24 Hours Postdose**

Sustained pain freedom from 2 to 24 hours postdose is defined as pain intensity of none at all time points from 2 to 24 hours postdose.

Participants who meet all the following criteria are classified as responders:

- Pain intensity of none at all time points from 2 to 24 hours postdose, i.e., in the 2 to 24-hour postdose analysis windows
- Missing pain intensity at  $\leq 1$  time point from 3 to 8 hours postdose, i.e., in the 3, 4, 6, or 8-hour postdose analysis windows
- No rescue medication taken at or before the pain intensity assessment in the 24-hour postdose analysis window.

Participants who are not responders are classified as failures. Failure criteria include any of the following:

- Rescue medication taken at or before 24 hours postdose (RM=F)
- Mild, moderate, or severe pain intensity at any time point from 2 to 24 hours postdose, i.e., in the 2, 3, 4, 6, 8, or 24-hour postdose analysis window
- Missing pain intensity at 2 or 24 hours postdose (NC=F), i.e., in the 2 or 24-hour postdose analysis window
- Missing pain intensity at  $> 1$  time point from 3 to 8 hours postdose (NC1=F), i.e., in the 3, 4, 6, or 8-hour postdose analysis window.

### **Sustained Pain Freedom from 2 to 48 Hours Postdose**

Sustained pain freedom from 2 to 48 hours postdose is defined as pain intensity of none at all time points from 2 to 48 hours postdose.

Participants who meet all the following criteria are classified as responders:

- Pain intensity of none at all time points from 2 to 48 hours postdose, i.e., in the 2 to 48-hour postdose analysis windows
- Missing pain intensity at  $\leq 1$  time point from 3 to 8 hours postdose, i.e., in the 3, 4, 6, or 8-hour postdose analysis windows
- No rescue medication taken at or before the pain intensity assessment in the 48-hour postdose analysis window.

Participants who are not responders are classified as failures. Failure criteria include any of the following:

- Rescue medication taken at or before 48 hours postdose (RM=F)
- Mild, moderate, or severe pain intensity at any time point from 2 to 48 hours postdose, i.e., in the 2, 3, 4, 6, 8, 24, or 48-hour postdose analysis window
- Missing pain intensity at 2, 24, or 48 hours postdose (NC=F), i.e., in the 2, 24, or 48-hour postdose analysis window
- Missing pain intensity at  $> 1$  time point from 3 to 8 hours postdose (NC1=F), i.e., in the 3, 4, 6, or 8-hour postdose analysis window.

### **Pain Relapse from 2 to 48 Hours Postdose**

Pain relapse from 2 to 48 hours postdose is defined as pain intensity of mild, moderate, or severe at any time point after 2 hours postdose for the subset of participants with pain freedom (i.e., pain intensity of none) at 2 hours postdose.

Participants who meet all the following criteria are classified as non-relapsers:

- Pain intensity of none at all time points after 2 hours postdose, i.e., in the 3 to 48-hour postdose analysis windows
- No rescue medication taken at or before the pain intensity assessment in the 48-hour postdose analysis window.

Participants who are not non-relapsers are classified as relapsers. Relapse criteria include any of the following:

- Rescue medication taken at or before 48 hours postdose (RM=F)
- Mild, moderate, or severe pain intensity at any time point after 2 hours postdose, i.e., in the 3, 4, 6, 8, 24, or 48-hour postdose analysis window

- Missing pain intensity at any time point after 2 hours postdose (NC=F), i.e., in the 3, 4, 6, 8, 24, or 48-hour postdose analysis window.

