### **9.3.3. Secondary Endpoint(s)/Estimand(s) Analysis**

The EAS will be used for the analysis of the secondary endpoints. For endpoints based on a single time point, such as phonophobia freedom at 2 hours postdose, participants with missing data at a single time point will also be classified as failures. For endpoints based on multiple time points, such as sustained pain relief from 2 to 48 hours postdose, participants with missing data at (a) 2, 24, or 48 hours postdose, or (b) more than 1 time point from 3 to 8 hours postdose will also be classified as failures.

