### 5.3. Methods to Manage Missing Data

Missing data in analyses of binary endpoints are defined as follows:

- Non-Completer=Failure (NC=F): Participants with missing data at a single point are classified as failures. This missing data imputation method is applied to endpoints based on data from a single time point (e.g., co-primary endpoints) as the main analysis method.

- Non-Completer with missing data at more than 1 Time Point=Failure (NC1=F): Participants with missing data at >1 time point postdose in a specified time period are classified as failures. This missing data imputation method is applied to endpoints that are based on data from multiple time points (e.g., secondary endpoints of sustained pain freedom from 2 to 24 hours postdose) as the main analysis method.

In the sensitivity analysis of the co-primary endpoints, the following imputation strategies for missing data will be implemented.

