#### 6.2.14. Percentage of participants with pain relapse at any time point after 2 hours postdose

Pain relapse at any time point after 2 hours postdose is defined as pain intensity of mild, moderate, or severe at any time point after 2 hours postdose for participants with pain intensity of none at 2 hours postdose.

- Estimand strategy: Composite policy (Section 2.2.2).
- Analysis set: EAS (Section 4). Participants with pain freedom at 2 hours postdose will be included.
- Analysis methodology: The Mantel-Haenszel risk estimation stratified by country/region will be used. See details in Section 5.2.2.
- Intercurrent events and missing data: (1) Taking rescue medication at or before 48 hours postdose (RM=F; see Appendix 2.1) and (2) missing pain intensity at >1 time point from 3 to 48 hours postdose (NC1=F; see Section 5.3 for definition) will be regarded as failures.

Treatment group comparisons of the percentage of participants with pain relapse at any time point after 2 hours postdose (i.e., in the 3 to 48 hour postdose analysis window) will present similar statistics as the main analysis of the co-primary endpoint of pain freedom (see Section 6.1.1.1).

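### The SAP gives two different missing-data rules for pain relapse, the protocol implies a third, and they disagree for any participant with exactly one missing diary value

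*SAP*

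**What the plan says.** The relapse analysis takes efficacy-set participants who are pain-free at 2 h and asks whether pain returns at 3, 4, 6, 8, 24 or 48 h. Missing values are handled differently from place to place.

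- **SAP Appendix 2.1.1** (Pain Relapse from 2 to 48 Hours Postdose) lists this as a criterion for relapse: "Missing pain intensity at any time point after 2 hours postdose (NC=F". It also says "Participants who are not non-relapsers are classified as relapsers", and its non-relapser definition allows no gap.
- **SAP 6.2.14** instead says "missing pain intensity at >1 time point from 3 to 48 hours postdose (NC1=F; see Section 5.3 for definition) will be regarded as failures".
- **SAP Appendix 1**, pain relapse row, agrees with 6.2.14: "missing pain intensity at >1 time point from 3 to 48 hours postdose will be regarded as failures".
- **SAP 5.3** defines NC1=F generally: "Participants with missing data at >1 time point postdose in a specified time period are classified as failures". It assigns NC1=F to endpoints built on several time points and NC=F to endpoints built on one.
- **Protocol 9.3.3** has a general rule. It opens "For endpoints based on multiple time points, such as sustained pain relief from 2 to 48 hours postdose" and counts as failures "participants with missing data at (a) 2, 24, or 48 hours postdose, or (b) more than 1 time point from 3 to 8 hours postdose". It does not name relapse.

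SAP 2.1, the place for departures from the protocol, lists none.

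**The concern.** One endpoint has two incompatible derivations inside the SAP, and nothing ranks them. Two programmers working from different sections could each follow the SAP and still produce different relapse tables, each with a confidence interval and p-value.

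The conflict also reaches a neighbouring endpoint. Take a participant who is pain-free at 2 h, misses only the 6 h entry, reports no pain at every other time and takes no rescue. Appendix 2.1.1 makes this person a responder for sustained pain freedom from 2 to 48 h and also a relapser over the same hours. The opposite mismatch arises under 6.2.14: a participant who misses only the 48 h entry fails sustained pain freedom, yet does not meet the missing-data criterion for relapse.

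If the conflict is left open until treatment codes are known, the choice of rule could be influenced by the results.

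**Working it through.** **Rules compared.** Call them A (Appendix 2.1.1: any of the six values missing), B (6.2.14, Appendix 1, 5.3: more than one of the six missing) and C (Protocol 9.3.3 applied to relapse: 24 or 48 h missing, or more than one of 3, 4, 6, 8 h missing). The 2 h condition in Protocol 9.3.3 has no effect here, because the relapse population has a 2 h value by definition.

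**Where they differ.** Consider a participant with no observed pain after 2 h and no rescue. Six time points give 2^6 = 64 missingness patterns. A makes 63 of them relapsers, B 57 and C 59. The disagreement is confined to the six patterns with exactly one gap:

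| Only missing value | A | B | C |
|---|---|---|---|
| 3, 4, 6 or 8 h | relapser | non-relapser | non-relapser |
| 24 or 48 h | relapser | non-relapser | relapser |

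**Size.** The plan gives no relapse rate and no missing rate, so there is no stated figure to reproduce. Assumptions: missingness m per time point, independent across time points; 40% of participants relapse by observed pain or rescue. With q = 1 − m, the probability of being called a relapser through gaps alone is:

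- A: 1 − q^6
- B: 1 − q^6 − 6m q^5
- C: 1 − q^2 (q^4 + 4m q^3)

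Reported relapse is 0.40 + 0.60 × that probability.

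| m | Gaps alone A / B / C | Reported relapse A / B / C |
|---|---|---|
| 1% | 5.9 / 0.1 / 2.0% | 43.5 / 40.1 / 41.2% |
| 3% | 16.7 / 1.2 / 6.4% | 50.0 / 40.7 / 43.8% |
| 5% | 26.5 / 3.3 / 11.0% | 55.9 / 42.0 / 46.6% |

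**Denominators.** Protocol 9.5 gives 630 evaluable per group and 2 h pain-freedom rates of 23.2% and 15.1%. Expected relapse denominators are 630 × 0.232 = 146 (zavegepant) and 630 × 0.151 = 95 (placebo). At m = 3% the A-to-B gap is 0.60 × (0.16703 − 0.01246) = 9.3 points, or about 14 zavegepant and 9 placebo participants.

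**Treatment difference.** Suppose true relapse is 40% in both groups, with m = 2% on zavegepant and 5% on placebo. The apparent difference (zavegepant − placebo) is 0.60 × the difference in gap probabilities:

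- A: 0.60 × (0.11416 − 0.26491) = −9.0 points
- B: 0.60 × (0.00569 − 0.03277) = −1.6 points
- C: 0.60 × (0.04184 − 0.11015) = −4.1 points

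Swapping the missing rates reverses every sign.

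**The case against.** The strongest reply is that the SAP's intent is clear enough. Sections 5.3 and 6.2.14 and Appendix 1 agree on more than one missing value, and 6.2.14 cites 5.3 for missing data, sending the reader to Appendix 2.1 only for the rescue rule. Appendix 2.1.1 would then be an outlier to correct. This has weight in showing that the SAP can be made consistent by changing one place. It does not remove the conflict. Appendix 2.1.1 is the section that sets out endpoint derivations, it is strict in both its relapser and non-relapser lists, and it omits the one-gap allowance written for every sustained endpoint beside it, so it does not read as a single slip of wording.

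A second reply is that Protocol 9.3.3 is not a relapse rule at all. It is a general sentence with sustained pain relief as its example, and Protocol Section 9 lets the SAP modify what the protocol outlines. That stands in part: the third rule is implied rather than stated. But SAP 2.1 declares no modification.

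A third reply concerns size. The missing rates are assumed, and gaps may cluster. A participant who misses both 6 h and 8 h is a relapser under all three rules, so clustering would shrink the disagreement. That stands.

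**Conclusion.** The contradiction is real and should be fixed, but its reach is limited. Pain relapse lies outside the testing hierarchy (Protocol 9.1.2, SAP 5.1) and its p-value is descriptive. Co-primary and key secondary conclusions and type I error are unaffected.

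The three rules give different relapse rates only if some participants have exactly one missing value with no observed pain or rescue; without such participants they agree. Under the illustrative 3% missingness and 40% relapse, the spread is 50.0%, 40.7% and 43.8%. It rests on independence and on two rates that the documents do not give.

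A reader might infer three stronger things that the documents do not support:

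- That the relapse rate under Appendix 2.1.1 would mostly measure diary compliance. In the 3% illustration, 10 of the 50 reported points come from gaps; at 5% it is 15.9 of 55.9.
- That the rule dilutes the treatment effect. That would follow from equal missingness in both groups; with unequal missingness the bias can go either way.
- That single gaps, for example from sleep, will be the usual pattern. No section reports missingness patterns, and sleep could equally produce consecutive gaps.

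**What to change.** Before unblinding, put one missing-data rule for relapse in SAP 6.2.14, Appendix 1 and Appendix 2.1.1, including the non-relapser definition in the last. In 6.2.14 and Appendix 1, replace the word failures with a statement that these participants are classified as relapsers, since failure is ambiguous when the event being counted is unfavourable.

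Either of two rules would resolve the conflict:

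- **Preferred: the Protocol 9.3.3 rule.** Relapse if pain above none is observed after 2 h, if rescue is taken by 48 h, if the 24 or 48 h value is missing, or if more than one of the 3, 4, 6 and 8 h values is missing. The sustained 2-to-48 h endpoints already use these missing-data conditions. Among participants pain-free at 2 h, relapse then becomes the exact complement of sustained pain freedom from 2 to 48 h. SAP 5.3 should note that 24 and 48 h are handled separately.
- **Alternative: keep the more-than-one rule of 5.3 and 6.2.14.** Correct both lists in Appendix 2.1.1 to match, and record the departure from Protocol 9.3.3 in SAP 2.1.

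The cost is SAP wording in a few places. No data collection, sample size or primary analysis changes.
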